6.4.3 Planned Analyses

Data will be analyzed using an intention-to-treat analytic approach. Depending on patterns of attrition or numbers of dyads participating in fewer than the planned 6 coaching sessions in each of the two PIE domains, we may additionally employ some post-hoc analytic approaches (e.g., comparisons of treated participants in each arm; including a covariate for number of sessions) to inform our understanding of the outcomes in this proof-of-concept study. The study outcomes based on the planned intention-to-treat analyses will be reported, with supplemental post hoc analyses reported if appropriate/informative.

Analyses will address one primary objective and three secondary objectives:

Primary:

1. Estimate the separate and combined effects of the two PIE intervention domains on dyadic engagement (primary outcome).

Secondary

2. Estimate the separate and combined effects of the two PIE intervention domains on infant intention communication.
3. Evaluate the *differential* changes in parent responsiveness following coaching on two individual Parents and Infants Engaged (PIE) intervention domains — responses to variable infant (a) sensory reactivity or (b) prelinguistic communication — as well as *cumulative* changes in parent responsiveness following coaching on both PIE domains.
4. Determine the extent to which (a) autonomic indices of infant self-regulation and (b) language, sensory reactivity patterns, response to joint attention, and social-communication skills change over the course of the PIE intervention. .

Overall analytic procedures:

All data will be cleaned and inspected for outliers, missing data and distributional irregularities. Although general linear modeling methods are robust to minor violations of distributional assumptions, appreciable departures from normality can compromise statistical tests and estimators. Where error distributions potentially deviate from normality or heteroscedasticity is suspected, the tests of the contrasts described below will be conducted using exact (resampling-based) nonparametric methods.

We will complete planned analyses of study outcomes using repeated measures analyses within a mixed modeling framework, to assess time and tx order effects, while

accommodating missing data and optimally utilizing all available data.

Although we are performing multiple statistical tests across outcomes and hypotheses in addressing the three specific aims, in this project is more important to avoid overlooking statistical signals of effectiveness of the novel intervention approach (type II errors), than avoiding false assertions of effectiveness (type I errors). We believe it is premature, therefore, to employ conservative adjustments to the type I error rates in statistical tests, which would compromise the power of statistical tests to detect such signals.

6.4.3.1 Primary Analyses

The primary objective of this study is to examine whether the novel PIE intervention transforms parent-infant transactions over time as intended, thereby facilitating increases in the time infants spend in dyadic engagement with their parents. We will also evaluate whether dyadic engagement outcomes differ based on whether parents are coached first in the sensory reactivity domain followed by coaching in the prelinguistic communication domain, or are coached in the opposite order.

Specifically, we will estimate the separate and combined effects of the two PIE intervention domains on dyadic engagement (primary outcome). H1a: At Posttest-1, dyads coached in either PIE domain will exhibit moderately more dyadic engagement compared to Baseline (Cohen's $d \geq .40$). H1b: At Posttest-2, dyads in both study arms will show additional small to moderate increases in dyadic engagement compared to Posttest-1 (Cohen's $d \geq .25$).

Our primary analysis will be conducted to explore a priori contrasts of interest within using repeated measures within a mixed modeling framework. Of key interest will be the contrast of Baseline to Posttest-1 scores and the contrast of Baseline to Posttest-2 scores (time effect). In addition, the model will include terms for treatment arm effects and treatment arm-by-time interactions. A time effect will indicate growth in the outcome from baseline to the posttest point, a zero or negligible time effect indicates stability, and a negative time effect suggests a drop in scores. A non-negligible treatment arm effect indicates that the two treatment arms differ on the outcome; while a non-negligible interaction coefficient suggests that the magnitude of change from baseline to the posttest point are not equivalent for members of the 2 treatment arms. Since the primary outcomes are proportions, arc sin transformations of these proportions will be performed before entering them into the models.

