6.4 Statistical Method

6.4.1 Statistical Design

The study is designed as a randomized comparative trial with two phases. For Study Phase 1, dyads will participate in baseline assessments; then eligible, consenting families will be randomized, stratifying by child age, to one of two treatment arms. Arm1 families will participate in initial coaching on the PIE sensory reactivity (SR) domain, and Arm2 families will participate in initial coaching on the PIE prelinguistic communication (PC) domain. Families will participate in 6 weekly coaching sessions in their respective treatment arms, and return for Posttest-1. For Study Phase 2, dyads in Arm1 will receive 6 weekly coaching sessions on the PC domain, and dyads in Arm2 will receive 6 weekly coaching sessions on the SR domain. Then families will return for Posttest-2.

Comparisons of dyads assigned to Arm1 and Arm2 at Posttest-1 will allow us to estimate the separate effects of the two domains of PIE coaching, as dyads will have only been coached in one domain (responding to prelinguistic communication cues or sensory reactivity cues) prior to Posttest-1. At Posttest-2, we will get estimates of the additive effects of coaching in the second PIE domain, and be able to evaluate whether there are any effects of the order of coaching by comparing dyads in Arm1 to those in Arm2.

For analyses, we will utilize repeated measure analyses within a mixed modeling framework, to assess time and tx order effects, while accommodating missing data and optimally utilizing all available data.

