6.4.3.2 Secondary Objectives Analyses, if applicable

Secondary Objective Analyses

Objective 2. Estimate the separate and combined effects of the two PIE intervention domains on infant intention communication.

H2a: At Posttest-1, infants in both groups will show no more than modest gains in intentional communication (Cohen's $d < .25$).

H2b: At Posttest-2, infants in both groups will show moderate increases in intentional communication compared to Baseline (Cohen's $d \geq .40$).

Analyses: This outcome variable involves counts of infant intentional communication attempts. We expect the average number of counts to be sufficiently large (eg. ≥ 8) that a normal approximation to a Poisson error distribution will be appropriate; however, if not, Poisson or negative binomial regression methods, or nonparametric approaches may be employed. The analyses for Objectives 2 and 3 will use the same framework as for our primary Objective #1, that is, to evaluate a priori contrasts of interest within a repeated measures mixed modeling framework. We will examine the contrast of Baseline to Posttest-1 scores and the contrast of Baseline to Posttest-2 scores (time effect). In addition, the models will include terms for treatment arm effects and treatment arm-by-time interactions.

Objective 3. Evaluate the differential changes in parent responsiveness following coaching on two individual Parents and Infants Engaged (PIE) intervention domains — responses to variable infant (a) sensory reactivity or (b) prelinguistic communication — as well as cumulative changes in parent responsiveness following coaching on both PIE domains.

H3a: At Posttest-1, parents in both intervention arm will show increases in responses attuned to their infants' behaviors compared to Baseline, with parents coached in the sensory reactivity domain showing more responses attuned to infants' sensory reactivity, and parents coached in the prelinguistic communication domain showing more responses attuned to infants' signals of attention focus and communicative intent.

H3b: At Posttest-2 (after coaching in both PIE domains), there will be no between-arm differences in parent responses attuned to infant sensory reactions or prelinguistic communication leads, due to increases in parent responsiveness to the newly coached domain of infant behaviors.

Analyses: See analyses for Objective 2.

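### Primary hypothesis H1b concerns the gain from Posttest-1 to Posttest-2, but the contrasts named in section 6.4.3.1 are both changes from Baseline

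*Combined protocol and SAP*

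**What the plan says.** Section 6.4.3.1 gives two hypotheses for dyadic engagement. H1a compares Posttest-1 with Baseline (d of at least .40). H1b has a different reference point: "H1b: At Posttest-2, dyads in both study arms will show additional small to moderate increases in dyadic engagement compared to Posttest-1", with d of at least .25.

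The next paragraph describes a repeated-measures mixed model with terms for time, arm and arm by time, and picks out the contrasts: "Of key interest will be the contrast of Baseline to Posttest-1 scores and the contrast of Baseline to Posttest-2 scores (time effect". Both model terms are then interpreted from the same starting point. For time: "A time effect will indicate growth in the outcome from baseline to the posttest point". For the interaction, a non-negligible coefficient is said to suggest that "the magnitude of change from baseline to the posttest point are not equivalent for members of the 2 treatment arms".

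Two other places bear on the point. Section 6.4.1 says "At Posttest-2, we will get estimates of the additive effects of coaching in the second PIE domain", but links this to no contrast. Section 6.4.3 provides a fallback for non-normal or heteroscedastic errors, under which "the tests of the contrasts described below will be conducted using exact (resampling-based) nonparametric methods". No section names a Posttest-1 to Posttest-2 contrast.

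**The concern.** The hypothesis and its analysis have different reference points. Baseline to Posttest-2 is the sum of the phase 1 and phase 2 gains, so a large first-phase gain can make it significant when nothing further happened in phase 2. A team following the contrast sentence literally would report two changes from Baseline, and could take a significant Posttest-2 time effect as support for H1b.

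The neighbouring text suggests how the mismatch arose. Section 6.4.3.2 uses the same two contrasts for Objective 2, where they fit: "H2b: At Posttest-2, infants in both groups will show moderate increases in intentional communication compared to Baseline". H1b is stated against Posttest-1, and the analysis sentence was not adapted to it.

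What is at stake is the pre-specified analysis of one of two primary-outcome hypotheses, in a trial whose section 6.4.2 values effect-size estimates for a later efficacy trial above significance tests. The second-phase change is one of those estimates.

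**Working it through.** **Inputs.** Section 6.4.2: 40 dyads with complete data, 20 per arm; type I error .05; correlation among repeated measures .3 to .7 (I add .5 as a midpoint). Section 6.4.3.1: d = .40 for H1a and d = .25 for H1b. Assumptions of mine: two-sided tests, equal SDs and equal correlations across timepoints, d in raw-score SD units.

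**The plan's own figures.** Section 6.4.2 gives effects detectable with .80 power as f = .37 to .42 for arm, and .27 to .18 for time and time by arm. With m measurements and N = 40, the noncentrality is f²Nm/(1+(m−1)r) for arm (df 1, 38) and f²Nm/(1−r) for the within-dyad effects (df m−1, 38(m−1)). With m = 2 this gives .367 and .419 for arm, and .269 and .176 for time, at r = .3 and .7. These round to the stated values. (With m = 3 they would be .332/.407 and .242/.158.) For a two-timepoint contrast f = d/2, so the plan's time effects correspond to d = 2 × .269 = .54 at r = .3 and 2 × .176 = .35 at r = .7. H1b's .25 lies below both.

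**What the named contrasts measure.** Write B, P1 and P2 for the mean outcome at the three timepoints.

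- H1a: P1 − B, which is named.
- Combined change: P2 − B = (P1 − B) + (P2 − P1), which is named.
- H1b: P2 − P1 = (P2 − B) − (P1 − B), which is not named but is estimable from the same model.

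**Can P2 − B stand in for H1b?** Take P1 − B = .40 SD and P2 − P1 = 0, so that H1b is false. Then P2 − B = .40 + 0 = .40 SD. Averaged over arms, the standard error is √(2(1−r)/40), and power comes from a noncentral t on 38 df.

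| r | SE | noncentrality .40/SE | power of Baseline to Posttest-2 |
|---|---|---|---|
| .3 | .187 | 2.14 | 55% |
| .5 | .158 | 2.53 | 69% |
| .7 | .122 | 3.27 | 89% |

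So the second named contrast would be significant more often than not with no second-phase gain at all.

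**Precision of the missing contrast.** The 95% half-width is t(.975, 38) = 2.024 times the SE. The per-arm SE is √(2(1−r)/20), with variance pooled across arms in the model (38 df).

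| r | half-width, averaged | half-width, per arm | power at d = .25, averaged |
|---|---|---|---|
| .3 | 2.024 × .187 = 0.38 SD | 2.024 × .265 = 0.54 SD | 26% |
| .5 | 2.024 × .158 = 0.32 SD | 2.024 × .224 = 0.45 SD | 34% |
| .7 | 2.024 × .122 = 0.25 SD | 2.024 × .173 = 0.35 SD | 51% |

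**The case against.** The strongest reply is that the plan already holds nearly everything needed. H1b sits inside the primary-analysis section with its timepoints, direction, arms and size. The model has time, arm and interaction terms over three measurements, so the contrast requires no new parameter. Section 6.4.1 intends to estimate the second domain's contribution at Posttest-2, section 6.4.2 promises descriptive summaries at both posttests, and calling two contrasts of key interest does not exclude a third. All of this stands, and it limits the consequence. It does not supply the contrast: section 6.4.1 names none, and section 6.4.3.1 reads both time and interaction as change from Baseline.

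A reader might infer more than the documents support in four ways.

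- *That H1b would have no interval or test at all.* That is too strict a reading, for the reasons above. Nor does the plan promise a confidence interval for any contrast, including the two it names.
- *That the resampling fallback excludes H1b.* Section 6.4.3 refers to contrasts described later, and H1b is itself a comparison described later. The text can be read either way, and the fallback is conditional.
- *That the undefined SD behind d, and the choice between the raw and the transformed scale ("arc sin transformations of these proportions will be performed before entering them into the models"), are faults of H1b.* The SD question applies to every hypothesis stated in d, and the scale question applies equally to H1a. They belong in a separate reporting comment.
- *That H1b demands significance in each arm, or that its low power is a defect found here.* No document sets such a rule or attaches a decision to any d, and section 6.4.2 already says the study is underpowered for smaller effects.

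**Conclusion.** The mismatch is real and should be fixed. One of two primary-outcome hypotheses is stated against Posttest-1, while the contrasts named for it are both against Baseline, and the second of these cannot substitute. With a phase 1 gain of .40 SD and no further gain, it would be significant with about 55% to 89% power while H1b is false. Those figures rest on 40 complete dyads, equal SDs, a common correlation of .3 to .7, d in raw-SD units and a two-sided .05 test. The textual point depends on none of them.

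The gap is one of pre-specification. Data, design, model and sample size are unaffected.

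**What to change.** In section 6.4.3.1:

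- Add Posttest-1 to Posttest-2, averaged over arms and by arm, as the analysis for H1b. Keep Baseline to Posttest-1 for H1a, and Baseline to Posttest-2 as the combined change.
- State that the added contrast is among those covered by the resampling fallback in section 6.4.3.
- Report it as an estimate with a 95% CI set beside d = .25, showing each arm next to the average.
- Describe it as second-phase change rather than the isolated effect of the second domain. Section 5.1 says phase 2 coaching also reviews the first domain, and section 6.2.1 acknowledges that the controls needed for an efficacy evaluation are absent. With no uncoached arm, maturation is part of the estimate.

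The cost is a few sentences and one set of contrast statements in the planned model. The drawback is imprecision: even averaged over arms at r = .7, the half-width (0.25 SD) is as large as the effect hypothesised, so the result will inform planning of a later trial more than it will settle H1b.

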5.2.2 Secondary and Exploratory Outcome Variables

Secondary outcome variables:

The first three secondary outcome measures will be assessed at three timepoints: Baseline, Posttest 1 (after families have been randomly assigned to an intervention arm and coached in one of the two PIE intervention domains), and Posttest 2 (after families have been coached in both of the PIE intervention domains). For these measures, we are particularly interested in whether there are effects specific to the initial PIE coaching domain (sensory

reactivity or prelinguistic communication) at Posttest 1, and whether there are order effects (differences between study arms) at Posttest 2.

1. Changes in parent responsiveness to infant sensory reactivity cues. [Measured via a project-developed rating tool.] This secondary measure is included to determine whether coaching in the sensory reactivity domain yields the expected specific effects on parents' responses to infant sensory reactivity cues. Parents will be rated on a 1-7 scale for their responsiveness to sensory reactivity for each of the 4 activities included in the parent-infant interaction session, using videorecordings of these sessions. A manual will be developed to describe the rating system and the level of responsivity associated with each of the 7 points on the scale. Research assistants will be trained to reliability by supervising staff. During rating of the project videos, one of 5 rated videos will be independently rated for reliability. Raters will be blind to study arm and timepoint of participants.
2. Changes in parent responsiveness to infant prelinguistic communication cues. [Measured via a project-developed rating tool.] This secondary measure is included to determine whether coaching in the prelinguistic communication domain yields the expected specific effects on parents' responses to infant prelinguistic communication cues. Manualization, training and reliability procedures are identical to those described for the parent responsiveness to sensory reactivity measure.

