3. Changes in infant intentional communication. [Measured via a project-developed coding system.] The rationale for including this outcome measure is that parental responsive support of infant engagement will promote infants' increased use of intentional communication, previously found to predict later receptive and expressive language outcomes for preschoolers already diagnosed with autism (Yoder et al., 2015). Intentional communication acts are defined as acts that are directed toward a communication partner (in this case, the parent or other primary family caregiver present during the parent-infant interaction session) to convey a message, and include (a) vocalizations, (b) gestures, or (c) combinations of both vocalizations and gestures. A coding manual will be developed to describe the coding system and provide examples and nonexamples of Infant intentional communication acts. This measure will be coded from videos of the parent-infant interaction sessions. Research assistants will be trained to reliability by supervising project staff. One of every five coded videos will be randomly selected for independent coding by another research assistant. Coders will be blind to assigned arm of the intervention and to timepoint of the assessment.

The following 8 secondary outcome variables will be measures at two timepoints: Baseline and Posttest 2. For these measures, we are particularly interested in examining the magnitude of change over the course of the full intervention, as well as whether there are order effects (differences between study arms) at Posttest 2.

4. Changes in infant respiratory sinus arrhythmia (RSA). This measure was chosen as an index of parasympathetic system functioning, and will be measured within a paradigm in which the infants are passively observing (a) an instrumental music video without social images, and (b) three on-minute vignettes of infant-directed speech, as an experimental analog of parent-infant interactions. We hypothesize we will see increased RSA levels during infant-directed speech, reflecting greater parasympathetic control and improved

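### The treatment arm term in 6.4.3.1 is not the arm difference at either posttest, and the plan does not say that the arm-by-time contrasts answer the posttest arm questions

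*Combined protocol and SAP*

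**What the plan says.** Dyadic engagement is measured at Baseline, Posttest-1 and Posttest-2 (5.2.1). Randomisation follows completion of the Baseline assessment (6.1.2).

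Section 6.4.3.1 specifies a repeated-measures mixed model. Its key contrasts are two time effects, Baseline to Posttest-1 and Baseline to Posttest-2. Arm and arm-by-time terms are added. The arm term is read without a time point: "A non-negligible treatment arm effect indicates that the two treatment arms differ on the outcome". The interaction is read as follows: "a non-negligible interaction coefficient suggests that the magnitude of change from baseline to the posttest point are not equivalent". Section 6.4.3.2 reuses these terms for Objectives 2 and 3, and for Objective 4 at Posttest-2 only. No section states the coding of arm and time.

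The posttest arm questions are set elsewhere. Section 6.4.1 says: "Comparisons of dyads assigned to Arm1 and Arm2 at Posttest-1 will allow us to estimate the separate effects" of the two coaching domains. For Posttest-2 it says the trial will "be able to evaluate whether there are any effects of the order of coaching by comparing dyads in Arm1 to those in Arm2". For the outcomes measured three times, 5.2.2 asks about domain-specific effects "at Posttest 1, and whether there are order effects (differences between study arms) at Posttest 2". For those measured twice it asks about the size of change, "as well as whether there are order effects (differences between study arms) at Posttest 2". Under Objective 3 in 6.4.3.2, H3a predicts domain-specific arm differences in parent responsiveness at Posttest-1, and H3b predicts none at Posttest-2.

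**The concern.** Comparing the arms at each posttest is how this trial separates the two coaching domains and checks for order effects. Someone writing the analysis program or the report has one sentence in 6.4.3.1 that says which coefficient shows that the arms differ, and it points to the arm term. Because Baseline is one of the outcomes, that coefficient does not answer the question at either posttest. An analyst who took the sentence literally could report a chance Baseline imbalance, or an average diluted by Baseline, as an arm effect.

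The coefficient that does answer the question is described in the same sentence, but it is not tied to the comparisons in 6.4.1. Used as it stands, it also gives up precision that the Baseline data could supply, in a trial that expects 20 dyads per arm.

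**Working it through.** **Inputs.** 20 dyads per arm with complete data, alpha .05, power .80 and correlations .3 to .7 (all from 6.4.2); three occasions for the primary outcome (5.2.1). Assumptions added here: equal SDs across occasions (set to 1 on the analysed scale), equal correlations, two-sided tests, and an illustrative true arm difference of .8 SD. Results are given in the order .3/.5/.7.

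**1. The plan's own figures.** For an F test on 1 and 38 df, 80% power needs a noncentrality of about 8.27. With N = 40 and m = 2 occasions:
- arm effect: f = √(8.27 × (1+ρ)/80) = .37 at ρ = .3 and .42 at ρ = .7;
- time and time-by-arm effects: f = √(8.27 × (1−ρ)/80) = .27 and .18.

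These match 6.4.2. With three occasions the values would be .33 to .41 and .24 to .16. The stated values are therefore correct for two occasions and conservative for three.

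**2. What the arm term estimates.** Let the true arm differences be 0 at Baseline (by randomisation), d1 at Posttest-1 and d2 at Posttest-2.
- Baseline as reference: the arm coefficient is the Baseline difference, with expectation 0. The two interaction coefficients have expectations d1 and d2.
- Sum-to-zero coding: the arm term is (0 + d1 + d2)/3. For (d1, d2) = (.8, 0), the pattern that H3a and H3b predict, it is .8/3 = .267. For (.8, .8) it is 1.6/3 = .533. For (.8, −.8) it is 0.

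Neither coding gives d1 or d2.

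**3. Precision of the contrasts that do answer the question.** The variance of a difference between two arm means is 2/20 = .1.
- Difference in change: SE = √(.1 × 2(1−ρ)) = .374/.316/.245.
- Common Baseline mean: SE = √(.1 × (1−ρ²)) = .302/.274/.226.
- Reduction in variance: 1 − (1+ρ)/2 = 35/25/15%.

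**4. Power for a true .8 SD difference (noncentral t).**
- Difference in change, 38 df: .8/SE = 2.14/2.53/3.27, giving 55/69/89%.
- Common Baseline, 37 df, SE multiplied by √(37/36) for estimating the Baseline slope: .8/SE = 2.62/2.88/3.49, giving about 72/80/93%.

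**5. Dependence on equal SDs.** Let k be the Baseline SD divided by the posttest SD. The variance of the change contrast relative to the adjusted one is 1 + (k−ρ)²/(1−ρ²). At k = 1 this is 1.54/1.33/1.18. At k = .7, chosen only as an illustration, it is 1.18/1.05/1.00. A narrower Baseline spread shrinks the gain and can remove it.

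**The case against.** The strongest reply is that nothing essential is missing. Section 6.4.1 names the arm comparison at both posttests. Section 6.4.3.1 describes a valid between-arm contrast for each posttest, the difference in change. Objective 3 is worded in terms of differential changes and 5.2.2 labels every secondary outcome a change, so that contrast fits the stated aims. For Objective 4 there is a single interaction coefficient and no ambiguity. The sentence on the arm term never says that it answers 6.4.1. Section 6.2.1 disclaims any evaluation of efficacy, and 6.4.2 puts descriptive arm summaries at both posttests ahead of the tests.

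Most of this stands, and it rules out several stronger inferences.
- A reader might infer that the plan has no way to compare the arms at a posttest. The interaction does so without bias.
- A reader might infer that reported arm effects will be chance Baseline differences. With Baseline-reference coding such a difference has an SD of √.1 = .32 and exceeds .25 SD in 43% of trials, but the plan states no coding, and a test of that term would still reject at 5%.
- A reader might infer power as low as 15 to 20% for the pattern predicted by H3a and H3b. That applies only if a sum-coded arm term were used for the posttest question, which the plan does not say it will do.
- A reader might infer that the power figures in 6.4.2 are wrong. They reproduce.

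The reply leaves two things unanswered: the only stated reading of the arm term is wrong for the posttest questions, and the link from 6.4.1 to the coefficient that answers them is not written down.

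**Conclusion.** The point holds as a correction to interpretation, with a gain in precision available. The arm term in 6.4.3.1, reused in 6.4.3.2, should not be read as the arms differing at a posttest. The arm-by-time contrasts are the valid answer and should be named as such. H1a and H1b are not affected.

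Estimating the contrasts with a common Baseline mean lowers their variance by 35/25/15% at correlations .3/.5/.7. This rests on 20 per arm, complete data, equal SDs and equal correlations. The gain is small at .7. It is least secure for the MSEL language scales and the SPA, which serve as Baseline entry cut-points (5.3), so equal SDs are doubtful there.

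**What to change.** In 6.4.3.1, replace the reading of the arm and interaction terms with wording such as:

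*The arm term will not be interpreted. The arm-by-time contrasts at Posttest-1 and at Posttest-2 answer the posttest arm questions in 6.4.1. Each is reported as sensory-reactivity-first minus prelinguistic-communication-first, with a 95% confidence interval.*

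Make the matching change in 6.4.3.2, with Posttest-2 only for Objective 4. Labelling by coaching content matters because 6.4.1 and 6.1.2 number the arms in opposite ways. Named contrasts also give the resampling fallback in 6.4.3 a definite arm comparison to test.

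Preferably, estimate these contrasts in a maximum-likelihood mixed model with one Baseline mean common to both arms. This is valid because randomisation follows Baseline. Use an unstructured covariance for the MSEL language and SPA outcomes.

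**Cost.** A few sentences, with the same data and software and no added covariate, so 6.4.4 stands. If the common-Baseline model is used throughout, within-arm changes use the pooled Baseline: the standard error of one arm's Baseline-to-Posttest-1 change goes from .265/.224/.173 to .240/.209/.167 SD, and Posttest-1 to Posttest-2 is unchanged. If arm-specific Baselines are wanted for H1a and the within-arm contrasts of Objectives 2 and 4, keep the existing model for those. If the resampling fallback, or the Poisson or negative binomial fallback, is used, the arm contrast must be written for that method too. Adding detectable single-posttest differences to 6.4.2 would help but is optional.
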